## **Hypotheses:**

Peripheral inflammatory mediators are differentially expressed in sub-populations of depressed patients, and such differences may represent indicators of responsiveness to anti-inflammatory treatment approaches.

**1a:** That aspirin augmentation will decrease HDRS scores versus placebo augmentation, and that a responder subgroup within the aspirin augmentation group will account for most of this signal.

**1b:** That aspirin augmentation will exert most of its clinical effect (steepest slope of change in HDRS) during the first 4 weeks of treatment.

**2:** That the serum inflammatory profile of the aspirin augmentation responders differs from the non-responders.

**2a:** That elevated IL-6 and TNF- $\alpha$  at study initiation will be associated with treatment response to aspirin.

**2b:** That IL-6 and TNF- $\alpha$  will be lower in the augmentation responders group versus the non-responders group after treatment.

**2c:** That higher ratios of TNF- $\alpha$ :IL-10 and IL-6:IL-10 will be associated with greater treatment response to aspirin.

**3:** That there will be different patterns of immunologic activation between treatment responders and non-responders, and within the treatment-responders group before and after treatment with aspirin.

**3a:** That the cytokines/chemokines assessed will show a different pattern of elevations in the aspirin-responder versus the aspirin non-responder group pre-treatment, and that the aspirin-responder group will show a differential pattern post- versus pre-treatment.

**3b:** That the peripheral inflammatory transcriptome will show altered patterns of immune gene expression in the aspirin-responder versus the aspirin non-responder group pre-treatment, and that the aspirin-responder group will show a differential pattern of gene expression post- versus pre-treatment.

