### I. Background and Significance:

Major depression is both common and burdensome, affecting over 15 million Americans in 2010 and costing over 210 billion dollars. Moreover, existing treatments for depression often do not achieve remission. Only a third of patients will achieve remission with their first antidepressant trial, and up to a third will not achieve remission even after multiple medication trials. Patients who do not respond to at least one antidepressant trial can be deemed treatment-resistant (although treatment-resistance exists along a continuum). It is possible that treatment resistant depression (TRD) may require novel treatment approaches. Many of the most frequently used pharmacologic treatments for depression target the monoamine systems or are hypothesized to exert an effect by affecting monoamine function, and other drugs under evaluation are generally focused on other neurotransmitter systems. A focus on other systems may yield additional treatment options for treatment-resistant depression.

Increasingly, converging lines of evidence support a role for inflammation in the pathogenesis of depression. Elevations in the inflammatory markers C-reactive protein (CRP) and interleukin-6 (IL-6) are found in patients with depression as compared to normal controls. Elevated levels of CRP can also predict the onset of depression, suggesting a role for inflammation in its pathogenesis. Tumor necrosis factor  $\alpha$  (TNF- $\alpha$ ), too, has been demonstrated to be elevated in major depression. When healthy volunteers are given endotoxin infusions, which stimulate the release of cytokines, the cytokine levels were associated with the development of mood disorder symptoms. Administration of exogenous cytokines including TNF- $\alpha$  and interferon- $\alpha$  (IFN-  $\alpha$ ) have produced classical symptoms of depression in previously mood-stable individuals. Finally, antidepressant treatment has been demonstrated to reduce levels of IL-6 and CRP in depressed patients, and a lack of response to treatment has been associated with persistent elevations in these inflammatory markers. Taken together, the above suggests a role for inflammation in the development of depression and given this, investigation of anti-inflammatory agents in the treatment of depression is indicated.

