## **II. Specific Aims:**

The primary aims of this study are:

**Aim 1:** To evaluate the clinical effect of aspirin augmentation on depression.

**Aim 1a:** To examine the effect of aspirin augmentation on depression symptoms (as measured by the Hamilton Depression Rating Scale) in comparison to placebo augmentation of antidepressant treatment.

**Aim 1b:** To examine the effect of aspirin augmentation on the rapidity of change in depression symptoms (as measured by the Hamilton Depression Rating Scale).

**Aim 2:** To assess with Luminex immunoassay the inflammatory profile of the blood of the aspirin augmentation responders compared with the non-responders.

**Aim 2a:** To determine whether elevated serum inflammatory cytokines IL-6 and TNF- $\alpha$  at study initiation are associated with treatment response to aspirin.

**Aim 2b:** To determine whether serum inflammatory cytokines IL-6 and TNF- $\alpha$  are lower in the augmentation responders group after treatment than in the augmentation non-responders group after treatment.

**Aim 2c:** To determine whether the ratios of TNF- $\alpha$ :IL-10 and IL-6:IL-10 are associated with treatment response versus non-response.

**Aim 3:** To evaluate in an exploratory fashion whether other cytokines/chemokines or immune gene expression patterns at study initiation are associated with subsequent antidepressant response to aspirin.

**Aim 3a:** To assess the panel of 60 cytokines/chemokines in the aspirin augmentation responders compared with the non-responders for potential contributions to treatment responsiveness. This analysis is exploratory.

**Aim 3b:** To assess with Fluidigm technology the blood of the aspirin augmentation responders compared with the non-responders for RNA from three flow sorted subsets of activated memory CD4 $^{+}$  (CD3 $^{+}$ CD44 $^{\text{hi}}$ ), and CD8 $^{+}$  (CD3 $^{+}$ CD44 $^{\text{hi}}$ ) T cells, as well as CD14 $^{+}$  monocytes. 96 T cell or monocyte-specific genes for pro-inflammatory, anti-inflammatory, chemokine, chemokine receptor, and signaling molecules will be measured. This analysis is exploratory.

**Aim 4:** To collect samples for eventual detailed immunologic characterization including antigen arrays and microRNAs.

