## **VI. Biostatistical Analyses:**

The baseline data to be collected and analyzed include: subject age at enrollment, gender, age of depression onset, number of previous depressive episodes, HDRS. HDRS will be repeated at the subsequent study visits for analysis. Cytokine levels will also be analyzed at the initial and final visits. The planned study end-point is at eight weeks after initiation, and is not based on any pre-determined treatment response. Exploratory analysis of the immunologic profiling data will be performed as well, with a goal to detect within-subject changes over the course of the study and to discern any differences between non-responders and responders.

Baseline measurements for continuous variables (e.g., age of onset, current age) will be assessed by t-test. Categorical measurements, such as gender, will be compared with Fisher's exact test or chi-square as appropriate. For the primary study outcome, the change in HDRS in the treatment versus control groups will be evaluated with analysis of covariance (ANCOVA), with initial HDRS score as a covariate.

Power calculations were based on a prior open-label trial of salicylic acid as an augmentation agent to fluoxetine, which found an average 15-point drop in HDRS score over a 4-week trial. To be conservative, we are assuming a much smaller effect size, and so this study is powered to detect a 3-point difference in HDRS score, a difference which is deemed to be clinically significant. 29 participants per group are required to detect this clinically significant difference assuming .80 power and a two-sided alpha of 0.05. Assuming a non-completion rate of approximately 20%, customary in clinical trials of antidepressants, we will enroll 74 subjects, anticipating 60 completers.

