Secondary outcomes will include the response of inflammatory biomarkers in treatment responders v. treatment non-responders at 8 weeks and the degree of biomarker association with antidepressant response. For this, the association of IL-6 and TNF- $\alpha$  at V1 with change in HDRS from V1 to V4 in the aspirin treated group versus the placebo treated group will be evaluated with an analysis of covariance (ANCOVA) model. This model will include three variables: treatment condition (aspirin versus placebo), baseline IL-6 or TNF- $\alpha$  level, and an interaction term (baseline cytokine value x treatment). A similar analysis of change in HDRS scores will be performed to assess the interaction of baseline TNF- $\alpha$  to IL-10 and IL-6 to IL-10 ratios by treatment condition. All applicable tests will be two-tailed with an alpha set at 0.05.

For our exploratory analysis of the full panel of 60 cytokines and chemokines, we expect to perform 60 comparisons and plan to use a false discovery rate approach. The interaction of the baseline value of each cytokine or chemokine with treatment condition will be evaluated. The interaction  $p$  values will be converted to FDR *adjusted p* values and ordered from smallest to largest. A cut point of 10% will be used to control the false discovery rate and to identify a subset of values that will be presumed to be biologically relevant. A similar procedure will be carried out for analysis of the 96 immune genes. All analyses were designed in consultation with a biostatistician.

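### The change clauses of exploratory hypotheses 3a and 3b look only within aspirin responders, and no placebo-controlled analysis of change is specified, so aspirin's effect could not be separated from mood improvement or time

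*Combined protocol and SAP*

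**What the plan says.** **Hypotheses.** Hypotheses 3a and 3b each have two clauses. The first is a baseline comparison; for 3a it predicts a "different pattern of elevations in the aspirin-responder versus the aspirin non-responder group pre-treatment". The second is about change. For 3a it is that the "aspirin-responder group will show a differential pattern post- versus pre-treatment"; for 3b it is that the "aspirin-responder group will show a differential pattern of gene expression post- versus pre-treatment". Parent hypothesis 3 places this change "within the treatment-responders group before and after treatment with aspirin". No change clause mentions placebo.

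**Status.** Under Specific Aims, Aims 3a and 3b each carry the label "This analysis is exploratory".

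**Analysis.** The Biostatistical Analyses section describes the exploratory work as having a purpose, "with a goal to detect within-subject changes over the course of the study and to discern any differences between non-responders and responders". It attaches no model or arm contrast to that purpose and does not confine it to aspirin subjects. For the 60 analytes it then says: "The interaction of the baseline value of each cytokine or chemokine with treatment condition will be evaluated". The resulting p values go through a false discovery rate (FDR) procedure with a 10% cut point, and the 96 genes are to be handled similarly.

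**Background.** The protocol reports that "antidepressant treatment has been demonstrated to reduce levels of IL-6 and CRP in depressed patients", and that failure to respond goes with markers that stay raised.

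**The concern.** The change clauses choose aspirin subjects by how their depression turned out and then compare them with their own baseline. If a marker moves with mood whatever causes the improvement, it will tend to move in this subgroup even when aspirin does nothing to it. The same holds for any drift over eight weeks that both arms share. The randomised placebo arm is what would separate these explanations, and no written analysis of change uses it.

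At stake is the meaning of the Aim 3 change results. A list of cytokines and genes that moved in aspirin responders could not show whether aspirin, recovery or time moved them. The primary HDRS comparison is unaffected.

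**Working it through.** **1. Does any specified analysis supply the missing contrast?**

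| Place | What it addresses | Uses placebo? | Addresses change? |
|---|---|---|---|
| Hypotheses 3a and 3b, first clause | Baseline, aspirin responders v non-responders | No | No |
| Hypotheses 3a and 3b, second clause | Post v pre, aspirin responders | No | Yes |
| Biostatistical Analyses, general goal | Within-subject change; responder differences | Not stated | Yes, without a model |
| Biostatistical Analyses, 60-analyte and 96-gene model | Baseline value x treatment | Yes | No |

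No row both uses placebo and specifies an analysis of change.

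**2. Plan's own figure.** There is no sample size, power or error rate for the change clauses, so there is nothing to reproduce for them. The plan gives 74 enrolled and about 20% non-completion: 74 x 0.8 = 59.2, in line with its 60 completers, or 30 per arm.

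**3. Illustration.** From the protocol: 30 completers per arm. Assumed, because the documents give no value: 35% response (30 x 0.35 = 10.5 responders); HDRS improvement and marker change standardised and jointly normal with correlation r = 0.2 to 0.5; no aspirin effect; two-sided 0.05 per marker before FDR adjustment.

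Taking responders as the top 35% on HDRS improvement:

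- Cut point z = 0.385; normal density there 0.370.
- Mean standardised improvement in responders: k = 0.370/0.35 = 1.058.
- Expected marker change in responders: r x k.
- SD of marker change in responders: sqrt(1 - r² x k x (k - z)), with k x (k - z) = 1.058 x 0.673 = 0.712.

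| r | Mean change | SD | Standardised change | Rejection, paired t-test, 10 or 11 responders |
|---|---|---|---|---|
| 0.2 | 0.212 | 0.986 | 0.215 | 9% to 10% |
| 0.5 | 0.529 | 0.907 | 0.584 | 38% to 42% |

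Simulation under the same assumptions gives about 10% and 39%. Comparing change between all aspirin and all placebo completers (30 v 30) rejects in about 5%. If a fall of 0.3 SD common to both arms is added, the simulated within-responder rate is about 33% to 73%, and the between-arm rate stays at about 5%.

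**4. A different parameterisation.** Fix the change in responders of both arms at d SD, and let response run from 20% to 50%. The within-responder test then rejects in 9% of trials (6 responders, d = 0.3) up to 95% (15 responders, d = 1.0). At 12 responders and d = 0.5 it is 35%. The comparison of all completers by arm rejects in about 3% to 5%.

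**The case against.** The strongest reply is that the protocol writes no formal pre/post test. The change clauses are predictions, the general goal is not limited to the aspirin arm, and the week-0 and week-8 cytokine draws are not limited by arm. This stands in part. A reader might infer that placebo samples will go unused, but the documents do not say so. What they show is an uncontrolled hypothesis with no controlled analysis attached.

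A reader might also infer that any change will be credited to aspirin. No attribution rule is written, the aims are exploratory, and the wording of hypothesis 3 may describe timing only. The text supports only that the two could not be separated.

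The Background covers IL-6 and CRP, not the rest of the panel or the genes. Subjects enter on a regimen unchanged for eight weeks, so a treatment-related fall cannot be assumed for every marker. Entry selects on HDRS and not on raised cytokines, so direct regression to the mean in the markers is weakly supported. Those limits are accepted.

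Finally, the rates are nominal. The FDR rule is written for the interaction p values. If it were extended to 60 pre/post tests, with analytes conditionally independent and sharing one r, per-analyte rejection at r = 0.2 would fall to about 0.7% (Benjamini-Hochberg) or 0.1% (Benjamini-Yekutieli); at r = 0.5 it would be 32% or 6%. The low end of the range then disappears. FDR still does not cure the confounding, because a fall that accompanies recovery is a real change and not a chance one. The exploratory label excuses low power and multiplicity, not a contrast that cannot answer the question.

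**Conclusion.** The point holds for the second clauses of hypotheses 3a and 3b and for the matching part of hypothesis 3. It does not extend to the baseline clauses or to the baseline-by-treatment model, which does use placebo. Followed as written, the change hypotheses would give results that cannot distinguish aspirin from mood improvement or time.

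The size is illustrative: about 10% to 40% rejection per marker with no aspirin effect, against about 5% between arms. It depends on the assumed response rate and correlations, and on nominal testing. The direction does not depend on the particular values, provided that marker change goes with improvement or with time. This is a cheap improvement to an exploratory aim.

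**What to change.** For each analyte, and for each gene with a week-8 sample, analyse the week-8 value (log scale for cytokines) by ANCOVA on treatment and baseline value in all randomised subjects with data. State the FDR family for these tests. This estimates the effect of assignment to aspirin on the marker, whatever the route.

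Treat change by response and arm as secondary. Response is a post-randomisation outcome, so aspirin responders against placebo responders is not a fully randomised comparison. It is also weak: with 15 down to 9 responders per arm, the difference detectable at 80% power is about 1.06 to 1.41 SD, against 0.74 SD with 30 per arm. Show aspirin-responder pre/post values as description only.

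Confirm that the week-8 follow-up samples include the gene-expression assay. The Study Visit 4 text refers only to detailed immunologic profiling, and the Visit 1 text uses similar words for the banked antigen and microRNA work.

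The cost is SAP wording and a little more analysis for the cytokines, since week-0 and week-8 draws are planned without restriction by arm. It may be more for the genes if week-8 assays are not planned. The downside is that a between-arm contrast is less likely to reach significance than a within-group one.

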## **III. Subject Selection:**

This study is a randomized, double-blind, placebo-control trial. The trial will enroll 74 adult subjects with treatment-refractory major depressive disorder, 37 per group. Assuming a non-completion rate of approximately 20%, as is customary in clinical trials of antidepressants, we will enroll a total of 74 subjects, anticipating 60 study completers. Subjects will all be recruited through outpatient psychiatric clinics affiliated with Brigham and Women's Hospital, through physician referral, print advertisements, and flyers.

Inclusion criteria:

- Aged 18-55
- Current diagnosis of major depressive disorder
- Hamilton Depression Rating Scale score of  $\geq 21$

- Stable treatment regimen (no medication changes or changes in psychotherapy treatment in past 8 weeks, and no participation in stepped treatments, such as completion of a course of cognitive behavioral therapy, during the trial)
- Failed to remit with up to 2 sequential antidepressant trials, or combination of 1 antidepressant and 1 augmentation agent
- Women of childbearing age must agree to use an approved method of contraception for the duration of the study

Exclusion criteria:

- Active suicidal ideation
- History of manic episodes or psychosis
- Alcohol or substance use disorder within the past 6 months
- Comorbid neurologic condition affecting the central nervous system
- Comorbid autoimmune condition
- History of thyroid disease or a current abnormal TSH
- Active or recent (within the past month) infection (such as otitis, pneumonia, urinary tract infection); temperature  $> 100.3$  or WBC count  $> 11$  K/microL will be considered evidence of active infection even in the absence of other symptoms
- History of GI bleed
- History of stroke
- History of a bleeding disorder
- Platelet count  $< 150,000/\text{mm}^3$  on initial screening
- On a blood-thinning agent or taking NSAIDs daily
- Current use of oral steroids or other immunomodulating medications
- Salicylate sensitivity
- Pregnancy or breastfeeding
- GFR less than  $60 \text{ mL/min}/1.73\text{m}^2$
- Current use of another nephrotoxic medication

The decision not to restrict participation to subjects utilizing a single medication was made to better reflect clinical practice, in which a variety of SSRI (selective serotonin reuptake inhibitors) and SNRI (serotonin-norepinephrine reuptake inhibitors) are used as first-line agents, and in order to enhance the generalizability of study findings.

#### **IV. Subject Enrollment:**

Subjects will all be recruited through outpatient psychiatric clinics affiliated with Brigham and Women's Hospital, through physician referral, print advertisements, and flyers. Demographics of the subjects are expected to largely reflect the referral patterns of these participating centers. Both males and females will be enrolled, however given the gender distribution in the prevalence of depression, it is expected that approximately 2/3 of the sample size will be female and 1/3 will be male. Contact information for the study coordinator will be provided by the physician in the case of a referral, and it will also be listed on the flyer and advertisement.

When potential subjects contact the study coordinator, they will first be asked a set of screening questions as outlined in the screening phone script. These questions will confirm that the subject

meets basic inclusion criteria. Subjects who are eligible at this time will be scheduled to attend the first baseline visit, where written informed consent will be obtained.

Details about the study, including objectives, procedures, and potential risks and discomforts will be discussed with the subject by the principal investigator ([name]) or a physician co-investigator. Subjects will be given the opportunity to ask any questions and will be given ample time to consider whether they wish to participate. They will be informed that refusal to participate will not interfere with their subsequent medical care.

During the first study visit, it will also be confirmed that the subject meets all other eligibility criteria, based on the clinical interviews and their laboratory results.

## **V. Study Procedures:**

The study design represents an 8-week randomized, placebo-control trial. The study procedures, as divided by study visits, are described below.

### Study Visit 1 (screening and study week 0):

At the first study visit, the principal investigator or co-investigator study physician will obtain informed consent. Details about the study, including objectives, procedures, and potential risks and discomforts will be discussed with the subject by a physician investigator. Subjects will be given the opportunity to ask any questions and will be given ample time to consider whether they wish to participate. They will be informed that refusal to participate will not interfere with their subsequent medical care.

The clinical study staff will then administer the Hamilton Depression Rating Scale (HDRS) and the Mini International Neuropsychiatric Interview (MINI) to confirm the subject has an active diagnosis of major depressive disorder (as defined by DSM V criteria) and rule out diagnoses of exclusion (namely mania, psychosis or hypomania). Subjects with active suicidal ideation, represented by a score of  $>2$  on HDRS item 3, will be ineligible for the study and will be referred for urgent or emergent clinical assessment as indicated in the safety plan. Subjects will complete the Quick Inventory of Depression Symptomatology-Self Report (QIDS-SR), the MGH Antidepressant Treatment Response Questionnaire, the Systematic Assessment for Treatment Emergent Events (SAFTEE), and the Childhood Experience of Care and Abuse Questionnaire (CECA-Q3). The QIDS-SR and SAFTEE are customary for antidepressant medication clinical trials. The CECA documents early life stressors that can both increase risk for depression and impact cytokine levels through the lifespan.

All subjects will have a complete blood count drawn to measure their white blood cell and platelet counts and a thyroid screening hormone test. Subjects will also have labs drawn to measure blood urea nitrogen, creatinine, and electrolytes. Subjects will be asked about co-morbid neurologic, rheumatologic, and bleeding disorders and recent history of infection. Subjects will be asked to report on their use of oral steroid medications, non-steroidal anti-inflammatory drugs (including aspirin, ibuprofen, naproxen, meloxicam, celecoxib, diclofenac, nabumetone, ketoprofen, and indomethacin), warfarin, heparin, and other anticoagulants (including clopidogrel, enoxaparin, rivaroxaban, apixaban, edoxaban, dabigatran, and fondaparinux).

Subjects will be asked to report on their age at first depression diagnosis, and number of depressive episodes, as well as existing treatments for depression, including names and dosages of medications, type(s) of psychotherapy, frequency of meetings with a psychiatrist, psychologist, social worker, or other counselor, and any other treatment modalities they engage in. Female subjects will also be asked to report whether they have regular monthly menstrual cycles, the date of their last menstrual period, and whether they are taking hormonal contraceptives or not. Women of child-bearing age will also receive a qualitative urine HCG pregnancy test. Female subjects will have blood drawn for follicle-stimulating hormone (FSH), estradiol, and progesterone levels. All subjects' temperature will be taken to assess for infection. If their temperature is greater than 100.3F, they will be excluded from the study. Subjects determined to be ineligible based on the results of the screening or screening labs will be thanked for their participation and conclude their participation.

Ten mL of subjects' blood will be separated by centrifuge and the serum analyzed for an array of 60 cytokines and chemokines including C-reactive protein (CRP), interleukin-6 (IL-6), and tumor necrosis factor alpha (TNF-alpha); assays will be performed using a Luminex bead-based immunoassay. Serum will be stored into small aliquots at -80°C to avoid repeated freeze-thaw cycles. 25 µl of serum per subject will be used for Luminex studies as previously reported. Expression data will be analyzed by Luminex software. All samples will be drawn between 8:00 AM and 10:00AM in order to minimize the effect of circadian fluctuations in cytokine levels. Subject's height and weight will be taken to allow for calculation of BMI; prior work has demonstrated a U-shaped relationship between BMI and pro-inflammatory cytokines, with higher values associated with underweight and obesity.

To evaluate gene profiles of peripheral immune cells, peripheral blood mononuclear cells (PBMCs) will be prepared by Ficoll-Paque PLUS gradient centrifugation from the blood in order to isolate T cells and monocytes. Frequency of CD4+, CD8+, and CD14+ cells will be measured. PBMCs will be stored into aliquots at -80°C. For transcriptomic analysis, Fluidigm Biomark technology will utilize microfluidic technology to perform high throughput gene expression measurements with real time PCR. RNA will be processed from flow cytometry-sorted activated/memory CD4+ (CD3+CD44hi), and CD8+ (CD3+CD44hi) T cells, as well as CD14+ monocytes. A panel of 96 T cell or monocyte-specific genes for pro-inflammatory, anti-inflammatory, chemokine, chemokine receptor, and signaling molecules will be measured.

To allow for the eventual, detailed characterization of the subjects' immunologic profiles, whole blood samples will also be banked for subsequent processing at the [name] Lab at Brigham and Women's Hospital/Harvard Medical School. The samples will be assayed for antigens using the following technique: over 500 individual antigens (proteins, lipids, myelin peptides) are spotted on slides by a robot, after which the slides are incubated with serum from subjects with depression and an immune signature is developed. The samples will also be assayed for microRNAs, non-coding RNAs that modulate immune function.

Subjects who meet inclusion criteria for the study will be given their pill packets for the ensuing 8 weeks, consisting of blister packs for a daily dose of aspirin 325mg in those randomized to the treatment condition and of blister packs of a placebo pill of the same size, shape, and color as the aspirin tablet in those randomized to the control condition. Subjects will be instructed to take

their pills in the evening before bed; in cardiovascular studies aspirin has had greater efficacy and better tolerability when taken at this time of day. Subjects will be instructed not to take aspirin over the counter during the study, and to inform study staff of their use of other over-the-counter anti-inflammatory medications. All subjects will be instructed to also continue their existing antidepressant treatment regimen but not to engage in new treatments or therapies during the course of the study. If new treatments are deemed clinically necessary during the course of the study subjects are instructed to contact study staff immediately to inform them of the change.

Study Visit 2 and 3 (weeks 2 and 4):

At study visits 2 and 3, subjects will be asked about their compliance with the study drug and about any adverse effects; they also will again complete the SAFTEE. They will be asked about any changes to their medications or psychiatric treatment. Study staff will re-administer the Hamilton Depression Rating Scale (HDRS) and subjects will again complete the QIDS-SR. Blood will be drawn for repeat cytokine/chemokine immunoassay, BUN, creatinine, and electrolytes measurements. If preferred, the subject can complete the psychometric measures by telephone and online portal and omit the blood draws at these visits.

Study Visit 4 (week 8):

At study visit 4, study staff will re-administer the Hamilton Depression Rating Scale (HDRS) and blood will again be drawn for repeat cytokine/chemokine immunoassay, including measures of CRP, IL-6, BUN, creatinine, electrolytes and TNF-alpha. Subjects will again complete the QIDS-SR and the SAFTEE, and will be asked about any changes to their medications or psychiatric treatment and any changes in their health status. Platelet count and FSH, estradiol, and progesterone levels as appropriate, will also be repeated. Follow up samples for the detailed immunologic profiling will also be drawn. Serum salicylate concentrations will be drawn (to confirm compliance with study medication in those subjects assigned to the aspirin condition, and to confirm subjects not assigned to the aspirin condition were not using it).

Subjects will be advised to follow up with their current outpatient psychiatric providers within two weeks of ending participation in the study.

Remuneration:

Subjects who complete the study including 4 in-person visits will receive a total of \$200 (\$45 for the first study visit, \$40 each for the second and third study visits (\$20 if no blood draw and subject completes questionnaires remotely), and \$75 for the last study visit) in four payments sent by mail after each visit. All participants will receive complementary parking for study visits.

Data storage:

At each study visit, the study staff will enter the data into case report forms in paper binders, as well as in our institution's research electronic data capture platform (REDCap). All laboratory values will be reviewed by a physician investigator. Paper files matching the case report forms in REDCap, and including the consent form, screening materials, and any additional correspondence will be stored in a locked filing cabinet in the office of the study staff at Brigham and Women's Hospital. All electronic study data will be stored securely on REDCap and de-identified prior to data analysis. Only group data will be reported.

